7.1.1.2 Myelodysplastic Syndrome Response Criteria

Response to treatment will be defined according to the modified International Working Group response criteria [Cheson et al, 2006] as outlined below.

- Complete Remission (CR)

For subjects to be classified as being in CR at a post-baseline visit, they must have all of the following maintained for a minimum of 4 weeks:

- Bone marrow evaluation: $\leq 5\%$ myeloblasts with normal maturation of all cell lines
- Peripheral blood evaluation:
 - Hemoglobin ≥ 11 g/dL
 - Platelets $\geq 100 \times 10^9/L$
 - Neutrophils $\geq 1.0 \times 10^9/L$
 - 0% blasts in blood

- Partial Remission (PR)

For subjects to be classified as being in PR at a post-baseline visit, they must have all CR criteria if abnormal before treatment except the following for a minimum of 4 weeks:

- Bone marrow blasts decreased by $\geq 50\%$ over pretreatment but still $> 5\%$
- Cellularity and morphology not relevant

- Marrow CR

For subjects to be classified as being in marrow CR at a post-baseline visit, they must have all of the following for a minimum of 4 weeks:

- Bone marrow: $\leq 5\%$ myeloblasts and decrease by $\geq 50\%$ over pretreatment
 - Peripheral blood: if HI responses, they will be noted in addition to marrow CR

- Hematologic Improvement (HI)

Requires 1 measurement of the following maintained for at least 8 weeks without ongoing cytotoxic therapy:

- HI – erythroid:

- Hemoglobin increase of ≥ 1.5 g/dL
or
- For RBC transfusions performed for hemoglobin ≤ 9.0 g/dL: reduction in RBC units transfused in 8 weeks by ≥ 4 units compared to the number of units transfused in the 8 weeks prior to treatment
- HI – platelets:
 - For pre-treatment platelet count of $>20 \times 10^9/L$ platelet, absolute increase of $\geq 30 \times 10^9/L$
 - For pre-treatment platelet count of $< 20 \times 10^9/L$, platelet absolute increase of $> 20 \times 10^9/L$ and $\geq 100\%$ increase from pre-treatment level
- HI – neutrophils:
 - Neutrophil count increase of $\geq 100\%$ from pre-treatment level and an absolute increase of $> 0.5 \times 10^9/L$

- **Relapse after CR or PR**
Requires at least 1 of the following:
 - Return to pre-treatment bone marrow blast percentage
 - Decrement of $\geq 50\%$ from maximum response levels in granulocytes or platelets
 - Transfusion dependence or hemoglobin level ≥ 1.5 g/dL lower than prior to therapy

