5.1 Inclusion Criteria

Subject is eligible for participation in the study if all of the following apply:

1. Institutional Review Board (IRB)/Independent Ethics Committee (IEC) approved written informed consent and privacy language as per national regulations (e.g., Health Insurance Portability and Accountability Act authorization [HIPAA] for US study sites) must be obtained from the subject or legally authorized representative prior to any study-related procedures (including withdrawal of prohibited medication, if applicable).
2. Subject is considered an adult according to local regulation at the time of signing the ICF.
3. Subject diagnosed with R/R AML or R/R higher risk MDS is defined as:
 - R/R AML
 - Morphologically documented primary or secondary AML by the WHO criteria (2016),
AND
 - Refractory to at least 2 cycles of induction chemotherapy/not a candidate for re-induction OR relapsed after achieving remission with a prior therapy,
AND
 - Received all standard therapies including targeted therapies (unless the therapy is contraindicated or intolerable) which are known to provide clinical benefit in the opinion of the investigator,
AND
 - Received salvage therapy OR is not a candidate for salvage therapy
 - R/R Higher Risk MDS
 - Has MDS by the WHO criteria (2016),
AND

- Either relapsed after achieving remission or refractory to standard therapies, including ≥ 4 cycles of hypomethylating agents (unless the therapy is contraindicated or intolerable),
AND
- Is classified as higher risk MDS with a score of > 3.5 by Revised International Prognostic Scoring System (IPSS-R) in MDS

4. Subject has an Eastern Cooperative Oncology Group (ECOG) performance status of ≤ 2 .
5. Subject must meet the following criteria as indicated on the clinical laboratory tests during screening period:
 - Serum AST and ALT $\leq 2.5 \times$ upper limit of normal (ULN)
 - Serum total bilirubin (TBL) $\leq 1.5 \times$ ULN
 - Serum creatinine $\leq 1.5 \times$ ULN or an estimated glomerular filtration rate of > 50 mL/min as calculated by the Modification of Diet in Renal Disease equation
 - Platelets $\geq 50,000/\mu\text{L}$ at cycle 1 day 1 (C1D1) in the dose escalation cohort only
6. Subject has a life expectancy of ≥ 12 weeks at the time of screening in the opinion of the investigator.
7. Subjects with AML must have peripheral blood absolute blast count of $< 20,000/\mu\text{L}$ at C1D1.

Note: Blast count can be controlled by hydroxyurea during screening period.

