9.4.1 Analysis of Primary Endpoint

9.4.1.1 Primary Analysis

CRc rate is defined for AML subjects as the number of subjects who achieve the best response of CRc (CR, CRp or CRi) divided by the number of subjects in the analysis population.

Response to treatment will be defined per modified Cheson criteria [Cheson et al, 2003].

CR + BM CR + PR rate is defined for MDS subjects as the number of subjects who achieve the best response of CR + BM CR + PR divided by the number of subjects in the analysis population. Response to treatment will be defined per Cheson criteria [Cheson et al, 2006].

Response rates will be calculated and its 90% confidence interval will be constructed by Clopper-Pearson method by dose level for phase 1 and by dose level and disease type for phase 2.

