    - Bone marrow blasts decreased by  $\geq 50\%$  over pretreatment but still  $> 5\%$
    - Cellularity and morphology not relevant
  - Marrow CR: For subjects to be classified as being in marrow CR at a post-baseline visit, they must have all of the following for a minimum of 4 weeks:
    - Bone marrow:  $\leq 5\%$  myeloblasts and decrease by  $\geq 50\%$  over pretreatment
      - Peripheral blood: if HI responses, they will be noted in addition to marrow CR
  - Hematologic Improvement (HI): For subjects to be classified as having hematologic improvement (HI) at a post-baseline visit, they must have 1 measurement of the following, maintained for at least 8 weeks without ongoing cytotoxic therapy:
    - HI – erythroid:

- Hemoglobin increase of  $\geq 1.5$  g/dL or
- For RBC transfusions performed for hemoglobin  $\leq 9.0$  g/dL: reduction in RBC units transfused in 8 weeks by  $\geq 4$  units compared to the number of units transfused in the 8 weeks prior to treatment
- HI – platelets:
  - For pre-treatment platelet count of  $>20 \times 10^9$  /L platelet, absolute increase of  $\geq 30 \times 10^9$  /L
  - For pre-treatment platelet count of  $< 20 \times 10^9$  /L, platelet absolute increase of  $> 20 \times 10^9$  /L and  $\geq 100\%$  increase from pre-treatment level
- HI – neutrophils:
  - Neutrophil count increase of  $\geq 100\%$  from pre-treatment level and an absolute increase of  $> 0.5 \times 10^9$  /L
- Relapse after CR or PR: For subjects to be classified as relapsing after CR or PR requires at least one of:
  - Return to pre-treatment bone marrow blast percentage
  - Decrement of  $\geq 50\%$  from maximum response levels in granulocytes or platelets
  - Transfusion dependence or hemoglobin level  $\geq 1.5$  g/dL lower than prior to therapy
- Stable Disease (SD): For subjects to be classified as having Stable Disease (SD), they must fail to achieve at least PR but show no evidence of progression for  $>8$  weeks
- Progressive Disease (PD): For subjects to be classified as having Progressive Disease (PD), they must show blast level increases depending on prior levels as follows:
  - For patients with:
    - $<5\%$  blasts:  $\geq 50\%$  increase in blasts to  $> 5\%$  blasts
    - $5\%-10\%$  blasts:  $\geq 50\%$  increase to  $> 10\%$  blasts
    - $10\%-20\%$  blasts:  $\geq 50\%$  increase to  $> 20\%$  blasts
    - $20\%-30\%$  blasts:  $\geq 50\%$  increase to  $> 30\%$  blasts
  - Or any of the following:

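### Marrow CR, part of the MDS primary endpoint, can be met by a subject whose marrow is already at or below 5% blasts before treatment

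*Protocol*

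**What the plan says.** The MDS primary endpoint is the rate of CR, marrow (BM) CR or PR. Protocol 9.4.1.1 begins "CR + BM CR + PR rate is defined for MDS subjects as the number of subjects who achieve the best response of CR + BM CR" and adds PR; SAP 6.4.1 agrees.

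Protocol 7.1.1.2 says, of subjects "being in marrow CR at a post-baseline visit, they must have all of the following for a minimum of 4 weeks", and the marrow condition it then lists is "Bone marrow: $\leq 5\%$ myeloblasts and decrease by $\geq 50\%$ over pretreatment". SAP 5.1.1 opens its entry with "For subjects to be classified as being in marrow CR at a post-baseline visit" and sets the same two conditions. Neither entry has a pre-treatment threshold.

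In protocol 5.1, criterion 3 asks for WHO-defined MDS, relapse or refractoriness to standard therapy, and a risk score: "Is classified as higher risk MDS with a score of" more than 3.5 on the IPSS-R. No minimum marrow blast percentage is given.

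Under SAP 6.4 the derived response is primary and the investigator's response is supportive. The derivation uses central myeloblast counts, and when both aspirate and biopsy are present, both must qualify. The study has no comparator (protocol synopsis).

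Protocol 9.1 and 9.4.1.3 set the MDS design: null rate 12%, target 25%, stop at 0 of 12 or at 4 or fewer of 32, and 10 or more of 52 for efficacy. Stated power is about 0.83, with type I error controlled at 0.10.

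**The concern.** Marrow CR has an absolute part (5% or less) and a relative part (at least halved). A subject already at 5% or less meets the absolute part on entry, so only the relative part does any work. When the starting count is a few cells, a halving is also a few cells.

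Such a response counts the same as any other in the two futility looks and the 10-of-52 rule. Because the derived response is primary, the wording will be applied as written. In a single-arm comparison with a fixed 12%, misclassification of this kind goes straight into the observed rate. At stake is whether an MDS efficacy conclusion could rest partly on measurement noise in subjects without excess blasts.

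**Working it through.** **1. Does the wording admit the case?** A fall from 4% to 2% is (4 − 2)/4 = 50%, and 2% is within the 5% limit. Held for 4 weeks, it is a marrow CR. Protocol Table 2 schedules marrows on day 1 of 28-day cycles from cycle 2, so two consecutive marrows can satisfy the duration.

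**2. The plan's own figures.** Exact three-stage binomial calculation: continue past 12 subjects with 1 or more responses, continue past 32 with 5 or more, succeed with 10 or more of 52.

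- At 12%: stop at 12 with probability 0.88^12 = 0.216, stop at 32 with 0.465, fail at 52 with 0.242, succeed with **0.078**.
- At 25%: stop at 12 with 0.032, stop at 32 with 0.057, fail at 52 with 0.077, succeed with **0.835**.

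The stated 0.83 is reproduced and the 0.10 limit is respected.

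**3. Counting error with no true change.** Let the true blast fraction be π and the number of cells counted n (assumed to be 200 or 500; the documents give none). The baseline count X0 and two later counts X1 and X2 are independent Binomial(n, π). A false marrow CR needs X1 and X2 both at or below X0/2. Given a baseline count between 1 cell and 5% of n:

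P(false) = Σ P(X0 = b)·[P(X ≤ b/2)]² ÷ Σ P(X0 = b), summed over b from 1 to 0.05n.

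| True blasts | 200 cells | 500 cells |
|---|---|---|
| 1% | 17% | 5.6% |
| 2% | 7% | 1.5% |
| 3% | 3% | 0.4% |
| 4% | 0.8% | 0.02% |

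Without conditioning on a non-zero baseline, the 1%, 200-cell figure is about 15%. The problem sits at very low blast levels and almost vanishes by 4%.

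**4. Effect on the decision.** Let f be the share of MDS subjects at 5% or less before treatment, and q the chance that such a subject, otherwise a non-responder, meets the wording by error. Both are assumed. If the rate without these cases is 12%, then p = 0.12 + 0.88·f·q. For example, f = 30% and q = 10% give 0.12 + 0.88 × 0.03 = 0.1464.

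| f | q = 1.5% | q = 5% | q = 10% |
|---|---|---|---|
| 10% | 12.1%, 0.083 | 12.4%, 0.094 | 12.9%, 0.112 |
| 20% | 12.3%, 0.087 | 12.9%, 0.112 | 13.8%, 0.153 |
| 30% | 12.4%, 0.092 | 13.3%, 0.132 | 14.6%, 0.201 |

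Each cell gives p and the probability of declaring efficacy. That probability reaches 0.10 at p of about 12.6% (0.1259 unrounded), that is, when f·q is about (0.1259 − 0.12)/0.88 = 0.67%.

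**The case against.** The strongest objection concerns the reference rate. Step 4 adds false responders on top of 12%, which is right only if the 12% was set under a stricter marrow CR rule or a different blast mix. If 12% and 25% were both set under the present wording in a similar population, the comparison is like for like and the error rate is not inflated. The documents do not say which. This stands, and it rules out any claim of a demonstrated breach.

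The 4-week condition also matters: one low reading is not enough. So does the rule that aspirate and biopsy must both qualify when both exist. Step 3 models one count per visit, so it may overstate the noise for subjects with both samples. With 500 cells and blasts of 2% or more, q is at most 1.5%, and even a 30% share leaves the probability at 0.092.

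Two supports are weaker than they look. The SAP progression rule, under which "they must show blast level increases depending on prior levels as follows", has a class for less than 5% blasts. Because it refers to prior levels, it may describe marrows after a response and does not prove enrolment at that level. MDS PR requires blasts still above 5% after a halving, hence a baseline above 10%. That separates PR from deeper responses and is not clearly a baseline safeguard left out of marrow CR.

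Finally, protocol 7.1.1.2 presents its definition this way: "Response to treatment will be defined according to the modified International Working Group response criteria". Whether the cited source carries a baseline condition cannot be checked from these documents, and nothing here relies on it. None of these objections supplies the missing threshold.

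**Conclusion.** The gap is real. Neither document makes marrow CR depend on an abnormal pre-treatment marrow, and eligibility does not close the opening. It can inflate the MDS response rate, mainly through subjects at about 1 to 2% blasts. By how much depends on the share of such subjects, the cells counted and the rule behind the 12%, none of which is given. Over the assumed ranges the null rate becomes about 12.1 to 14.6% and the probability of declaring efficacy about 0.08 to 0.20. The margin is thin: a rise of 0.6 percentage points takes it to 0.10.

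A reader might infer that the type I error exceeds 0.10, or that the sample-size figures are wrong. The documents support neither: 0.078 and 0.835 are correct at 12% and 25%, and a breach would need assumptions the documents do not make. A reader might also take a fall from 4% to 2% as the typical false response. It meets the wording if held for 4 weeks, but counting error rarely produces it (0.8% or 0.02%). This is an inexpensive improvement to the endpoint definition, not a demonstrated loss of error control.

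**What to change.** In protocol 7.1.1.2 and SAP 5.1.1, count marrow CR toward the primary endpoint only when pre-treatment marrow myeloblasts are above 5%. Keep subjects at 5% or less in the FAS denominator, where they can still respond by CR. Report the rate under the present wording as a sensitivity row, and state which marrow CR rule and baseline blast mix lie behind 12% and 25%.

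If the sponsor keeps the present wording as primary because 12% and 25% were set under it, say so. Then make the sensitivity row the primary rate excluding marrow CRs with a baseline of 5% or less, and compare it with the 10-of-52 rule.

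The text change is one line in each document plus one table row. It does alter a primary endpoint in an open-label study with futility looks, so the reason and timing should be recorded. The observed MDS rate may be slightly lower. At the stated 12% and 25% the design figures do not change. If the 25% assumed the looser rule, power falls: to 0.794 if the target rate becomes 24%, and to 0.747 at 23%.

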### **5.1.6 Secondary Efficacy Endpoint: Objective Response Rate (ORR)**

Objective Response Rate (ORR) is defined as the number of subjects who achieve CR, BM CR, or PR or HI at any of the postbaseline visits divided by the number of subjects in the analysis population. ORR is applicable for MDS subjects only.

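### MDS hematologic improvement can be scored in a lineage that was never low, or on transfused values, which can bias the HI rate and ORR upward

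*Protocol*

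**What the plan says.** Protocol 7.1.1.2 sets the general rule for HI: "Requires 1 measurement of the following maintained for at least 8 weeks without ongoing cytotoxic therapy". The MDS part of SAP 5.1.1 has the same rule: "they must have 1 measurement of the following, maintained for at least 8 weeks without ongoing cytotoxic therapy". One lineage is enough. The routes are:

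- **Erythroid, by value:** a hemoglobin rise of at least 1.5 g/dL. There is no ceiling on the starting value and no transfusion-free interval.
- **Erythroid, by transfusion:** at least 4 fewer RBC units in 8 weeks. This route alone is tied to a low value; it begins "For RBC transfusions performed for hemoglobin" and sets 9.0 g/dL or below.
- **Platelets:** split at 20 x 10^9/L before treatment. Above 20, a rise of at least 30 suffices, with no upper limit on the starting count.
- **Neutrophils:** at least a doubling and an absolute rise above 0.5 x 10^9/L, with no ceiling on the starting count.

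The MDS PR definition in the same section does refer to the pre-treatment state: "they must have all CR criteria if abnormal before treatment except the following for a minimum of 4 weeks".

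HI alone makes a subject an objective responder. SAP 5.1.6 counts "the number of subjects who achieve CR, BM CR, or PR or HI at any of the postbaseline visits", and protocol 9.4.2 agrees. HI and ORR are both listed as MDS secondary endpoints in protocol Table 7.

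**The concern.** A change-from-baseline criterion measures improvement only if there was something to improve. MDS eligibility requires relapsed or refractory disease and an IPSS-R score above 3.5, but no cytopenia in any particular lineage. An anemic subject may therefore enter with normal platelets or neutrophils. A lasting upward shift in that normal lineage, or a single low baseline reading followed by ordinary readings, can then be scored as HI. A subject whose hemoglobin is kept 1.5 g/dL above baseline by more frequent transfusion also qualifies, although that is the opposite of improvement.

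The trial has no untreated arm from which a background HI rate could be estimated and subtracted. What is at stake is the interpretation of the HI rate and ORR as evidence of activity in MDS.

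**Working it through.** **1. The plan's own figure.** The documents give no target rate, power or sample size for HI or ORR. The nearest stated figure is the MDS design in protocol 9.1 and SAP 3: 25% against 12%, power about 0.83, type I error controlled at 0.10. Protocol 9.4.1.3 gives the rule: continue if responses exceed 0 of 12 and 4 of 32, and succeed with at least 10 of 52. Exact three-stage binomial summation gives power 0.835 and type I error 0.078, so the stated figures hold. The endpoint is CR + BM CR + PR. HI is not in it, so nothing below changes these numbers.

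**2. What the text admits**, each change being held for 8 weeks:

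- Platelets 250 to 280 x 10^9/L: rise of 30, meets at least 30.
- Hemoglobin 12.5 to 14.0 g/dL: rise of 1.5, meets at least 1.5.
- Neutrophils 2.0 to 4.0 x 10^9/L: 100% increase and a rise of 2.0, meets both conditions.

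All three starting values are above the plan's own MDS CR thresholds (100, 11 and 1.0).

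**3. How often noise alone meets the platelet route.** Simulation with no drug effect:

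- *From the documents:* one baseline value (SAP 6.1), threshold baseline + 30, every reading in a run spanning at least 56 days at or above it. Visit days follow protocol Table 2: days 2, 8, 15, 22, 29, 30, 36, 43, 50 and 57, then two-weekly to day 141. This grid fits cycles 3 onward, and also two cycles followed by 12 weeks of Observation Period 1.
- *Assumed:* independent, normally distributed readings around a constant mean, with within-subject CV of 8, 12 or 16%.

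| Mean platelets (x 10^9/L) | False HI to day 141 (CV 8 to 16%) | Follow-up ending at day 85 |
|---|---|---|
| 80 | 0-0.3% | 0-0.1% |
| 150 | 0.2-4% | 0.03-1.2% |
| 250 | 2-9% | 0.6-3.4% |

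False HI is close to zero where platelets are truly low and grows where they are normal, which is where a baseline condition would act.

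**4. How 'maintained' is confirmed.** With 12 visits and assumed within-subject SDs (hemoglobin 0.5-1.0 g/dL around 12.5, platelets 20-40 around 200, log neutrophils 0.3-0.5 around 3), false HI per lineage is:

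- below 0.1% to 3.6% if nine consecutive weekly visits must qualify;
- 0.1-12.5% if five consecutive two-weekly visits must qualify;
- 1.7-46% if two consecutive visits are taken as enough.

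The documents do not say which readings must qualify.

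**5. Illustrative effect on ORR.** If t is the true ORR and f the false-HI probability among the rest, observed ORR = t + (1 - t)f. Taking t = 12% for illustration only:

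- f = 2%: 0.12 + 0.88 x 0.02 = 13.8%.
- f = 9%: 0.12 + 0.88 x 0.09 = 19.9%.
- f = 10%: 0.12 + 0.88 x 0.10 = 20.8%, about 11 of 52 (90% Clopper-Pearson 12.3-32.6%) instead of 6 of 52 (5.1-21.5%).

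The 2% and 9% cases would require every non-responder to have platelets near 250, so they do not estimate this population.

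**6. The transfusion route.** No rate can be calculated, because the documents give no transfusion frequencies. The 8-week rule does not block it, since regular transfusion can sustain a level. Elsewhere the plan does guard against transfusion: AML CR needs one week free of RBC and platelet transfusion (protocol 7.1.1.1), and SAP 5.1.1 counts a transfusion after an HI response as progression. Neither prevents HI from being credited on transfused values.

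**The case against.** A reader might infer that the reported ORR will be inflated by a known amount. The documents do not support that. They give no baseline distribution of counts, and protocol 2.1 itself describes MDS as a disease of peripheral cytopenias, so many subjects may sit where false platelet HI is near zero. The 8-week rule combined with the near-weekly visits of cycles 1 and 2 removes most random fluctuation. Relapse, progression or new therapy ends the observation period, so full follow-up for everyone is generous. Larger percentages arise only if fewer readings are allowed to stand for the 8 weeks. All of this stands, and it limits what can be said about size.

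A reader might also infer that the efficacy conclusion is at risk. It is not: HI is outside the primary MDS endpoint and the BOP2 boundaries, and ORR is reported with a 90% interval and no decision rule. HI has its own rate and ranks lowest among the MDS responses in SAP 5.1.5, so HI-only responders can be separated and their listed baselines inspected.

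Finally, both documents cite published response criteria, which might contain pre-treatment thresholds. That cannot be checked from these documents. If so, the omission is one of transcription, but the definitions printed in both documents still lack the condition.

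None of this supplies a baseline or transfusion condition.

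**Conclusion.** The gap is real and identical in both documents. Three of the four HI routes lack a low-baseline condition, and the hemoglobin and platelet routes accept transfused values. Followed exactly, the plan would score a sustained rise in a normal lineage, or a transfusion-supported hemoglobin, as HI and as objective response. The likely direction is upward, for two descriptive MDS secondary endpoints.

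The amount is unknown. The platelet figures rest on assumed CVs of 8-16%, independent readings and a constant underlying mean; slow drift would make sustained false rises more common, and shorter follow-up less common. They cover one lineage and exclude transfusion. The matter deserves correction because the fix is simple, but it does not threaten the primary MDS analysis.

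**What to change.** Make the same changes in protocol 7.1.1.2 and SAP 5.1.1:

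1. Assess HI only in lineages below the plan's own MDS CR thresholds at baseline: hemoglobin below 11 g/dL, platelets below 100 x 10^9/L, neutrophils below 1.0 x 10^9/L.
2. Keep subjects with no eligible lineage in the ORR denominator; they can still respond by CR, BM CR or PR.
3. Define 'maintained' as every scheduled reading across the 8 weeks meeting the criterion.
4. For post-baseline hemoglobin and platelets, do not credit readings within 7 days after a transfusion of the relevant product, and say whether such a reading breaks the run or is skipped. Seven days is the interval already used for AML CR. Limiting this to post-baseline values avoids losing the single baseline reading.
5. Align SAP 6.2.5, which records transfusions only through end of treatment, with SAP 5.1.11, which uses them to the end of Observation Period 2. SAP 6.2.5 also starts 28 days before cycle 1, whereas the RBC-unit route needs the 8 weeks before treatment.

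HI also appears among the clinical-benefit outcomes in protocol 4.1.1. These changes concern the endpoint derivation only; the sponsor should state whether the two uses share one definition.

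Cost: items 1 to 3 need a few words and a programming condition on counts already collected. Items 4 and 5 need transfusion records through the observation periods, so the sponsor should confirm that they exist. HI and ORR may come out lower, and somewhat fewer readings will be usable.
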